### 8.1 Administrative and General Procedures

#### 8.1.1 Informed Consent

The investigator or medically qualified designee (consistent with local requirements) must obtain documented consent from each potential participant or each participant's legally acceptable representative prior to participating in a clinical study or future biomedical research. If there are changes to the participant's status during the study (eg, health or age of

majority requirements), the investigator or medically qualified designee must ensure the appropriate consent is in place.

#### **8.1.1.1 General Informed Consent**

Consent must be documented by the participant's dated signature or by the participant's legally acceptable representative's dated signature on a consent form along with the dated signature of the person conducting the consent discussion.

A copy of the signed and dated consent form should be given to the participant before participation in the study.

The initial ICF, any subsequent revised written ICF, and any written information provided to the participant must receive the Institutional Review Board/Independent Ethics Committee's (IRB/IEC's) approval/favorable opinion in advance of use. The participant or his/her legally acceptable representative should be informed in a timely manner if new information becomes available that may be relevant to the participant's willingness to continue participation in the study. The communication of this information will be provided and documented via a revised consent form or addendum to the original consent form that captures the participant's dated signature or by the participant's legally acceptable representative's dated signature.

Specifics about a study and the study population will be added to the consent form template at the protocol level.

The informed consent will adhere to IRB/IEC requirements, applicable laws and regulations, and Sponsor requirements.

#### **8.1.1.2 Consent and Collection of Specimens for Future Biomedical Research**

The investigator or medically qualified designee will explain the future biomedical research consent to the participant, answer all of his/her questions, and obtain written informed consent before performing any procedure related to the future biomedical research substudy. A copy of the informed consent will be given to the participant.

#### **8.1.2 Inclusion/Exclusion Criteria**

All inclusion and exclusion criteria will be reviewed by the investigator who is a qualified physician to ensure that the participant qualifies for the study.

#### **8.1.3 Participant Identification Card**

All participants will be given a participant identification card identifying them as participants in a research study. The card will contain study site contact information (including direct telephone numbers) to be used in the event of an emergency. The investigator or qualified designee will provide the participant with a participant identification card immediately after the participant provides written informed consent. At the time of intervention allocation/randomization, site personnel will add the intervention/randomization number to the participant identification card.

The participant identification card also contains contact information for the emergency unblinding call center so that a healthcare provider can obtain information about study intervention in emergency situations where the investigator is not available.

#### **8.1.4 Medical History**

A medical history will be obtained by the investigator or qualified designee. Medical history will include all active conditions, and any condition diagnosed within the prior 10 years that are considered to be clinically significant by the investigator. Details regarding the disease for which the participant has enrolled in the study will be recorded separately and not listed as medical history.

#### **8.1.5 Prior and Concomitant Medications Review**

##### **8.1.5.1 Prior Medications**

The investigator or qualified designee will review prior medication use, including any protocol-specified washout requirement, and record prior medication taken by the participant within 28 days before the first dose of study medication.

##### **8.1.5.2 Concomitant Medications**

The investigator or qualified designee will record medication, if any, taken by the participant during the study.

All medications related to reportable SAEs and ECIs should be recorded as defined in Section 8.4.

All new anticancer therapy initiated after the study start must be recorded in the eCRF. If a participant initiates another anticancer therapy other than the assigned study treatment(s), the study treatment(s) should be discontinued and the participant will move into the Post-treatment Follow-up Phase; if a participant initiates a new anticancer therapy within 30 days after the last dose of the study treatment, the 30 day Safety Follow-up Visit should occur before the first dose of the new therapy.

#### **8.1.6 Assignment of Screening Number**

All consented participants will be given a unique screening number that will be used to identify the participant for all procedures that occur prior to intervention allocation. Each participant will be assigned only 1 screening number. Screening numbers must not be re-used for different participants.

Any participant who is screened multiple times will retain the original screening number assigned at the initial screening visit. Specific details on the screening/rescreening visit requirements are provided in Section 8.11.1.

### **8.1.7 Assignment of Treatment/Randomization Number**

All eligible participants will receive an allocation number (AN). The AN identifies the participant for all procedures occurring after randomization. Once an is assigned to a participant, it can never be re-assigned to another participant.

A single participant cannot be assigned more than 1 AN.

### **8.1.8 Study Intervention Administration**

During on-site visits, administration of study medication will be witnessed by the investigator and/or trial staff. The administration, the dose, the time of administration, as well as any immediate reactions at the time of intake will be documented in the eCRF.

For non-visit days, MK-8353 and selumetinib will be taken at home.

When a participant attends a study visit, he/she will bring any unused capsules.

#### **8.1.8.1 Timing of Dose Administration**

##### **8.1.8.1.1 MK-8353 Administration**

MK-8353 is an oral medication, and is supplied as hard-shell capsules in strength of 50 mg or 100 mg. Participants should be instructed to take MK-8353 capsule(s) in the morning and in the evening at approximately the same times every day.

MK-8353 will be taken BID for the repeated schedule of 4 days on followed by 3 days off.

The Pharmacy Manual contains specific instructions for MK-8353 storage and administration.

##### **8.1.8.1.2 Selumetinib Administration**

Selumetinib is an oral medication, and is supplied as hard-shell capsules in strength of 25 mg. Participants should be instructed to take selumetinib capsules in the morning and in the evening at approximately the same times every day. Selumetinib should be taken on an empty stomach; no food or drink other than water for approximately 2 hours prior to dosing and approximately 1 hour after dosing.

Selumetinib will be taken BID in a repeating cycle of 4 days on followed by 3 days off.

The Pharmacy Manual contains specific instructions for MK-5618 (selumetinib) storage and administration.

### **8.1.9 Discontinuation and Withdrawal**

Participants who discontinue study intervention prior to completion of the treatment period should be encouraged to continue to be followed for all remaining study visits.

When a participant withdraws from participation in the study, all applicable activities scheduled for the final study visit should be performed (at the time of withdrawal). Any AEs that are present at the time of withdrawal should be followed in accordance with the safety requirements outlined in Section 8.4 .

### **8.1.9.1 Withdrawal From Future Biomedical Research**

Participants may withdraw their consent for future biomedical research. Participants may withdraw consent at any time by contacting the principal investigator for the main study. If medical records for the main study are still available, the investigator will contact the Sponsor using the designated mailbox ([contact]). Subsequently, the participant's consent for future biomedical research will be withdrawn. A letter will be sent from the Sponsor to the investigator confirming the withdrawal. It is the responsibility of the investigator to inform the participant of completion of withdrawal. Any analyses in progress at the time of request for withdrawal or already performed prior to the request being received by the Sponsor will continue to be used as part of the overall research study data and results. No new analyses would be generated after the request is received.

In the event that the medical records for the main study are no longer available (eg, if the investigator is no longer required by regulatory authorities to retain the main study records) or the specimens have been completely anonymized, there will no longer be a link between the participant's personal information and their specimens. In this situation, the request for specimen withdrawal cannot be processed.

### **8.1.10 Participant Blinding/Unblinding**

This is an open-label study; there is no blinding for this study.

### **8.1.11 Calibration of Equipment**

The investigator or qualified designee has the responsibility to ensure that any device or instrument used for a clinical evaluation/test during a clinical study that provides information about inclusion/exclusion criteria and/or safety or efficacy parameters shall be suitably calibrated and/or maintained to ensure that the data obtained is reliable and/or reproducible. Documentation of equipment calibration must be retained as source documentation at the study site.

## **8.2 Efficacy Assessments**

### **8.2.1 Tumor Imaging and Assessment of Disease**

The process for image collection and transmission to the imaging contract research organization can be found in the Site Imaging Manual (SIM). Tumor imaging is strongly preferred to be acquired by CT. For the abdomen and pelvis, contrast-enhanced MRI may be used when CT with iodinated contrast is contraindicated, or when mandated by local practice. MRI is the strongly preferred modality for imaging the brain. The same imaging technique regarding modality, ideally the same scanner, and the use of contrast should be

used in a participant throughout the study to optimize the reproducibility of the assessment of existing and new tumor burden and improve the accuracy of the assessment of response or progression based on imaging.

Note: for the purposes of assessing tumor imaging, the term “investigator” refers to the local investigator at the site and/or the radiological reviewer located at the site or at an offsite facility.

Imaging of chest, abdomen, and pelvis is typical. The SIM will include detailed instructions for specific tumor types and clinical scenarios.

Although RECIST 1.1 references to a maximum of 5 target lesions in total and 2 per organ, Merck allows a maximum of 10 target lesions in total and 5 per organ, if clinically relevant to enable a broader sampling of tumor burden.

### **8.2.1.1 Initial Tumor Imaging**

Initial tumor imaging at the Screening Visit must be performed within 28 days prior to the date of allocation.

Tumor imaging performed as part of routine clinical management is acceptable for use as screening tumor imaging if they are of diagnostic quality and performed within 28 days prior to the date of allocation.

Participants with previously treated brain metastases may participate provided they have stable brain metastases (ie, without evidence of progression by imaging confirmed by MRI if MRI was used at prior imaging, or confirmed by CT imaging if CT used at prior imaging) for at least 4 weeks prior to the first dose of study intervention. Any neurologic symptoms must have returned to baseline and participants must have no evidence of new or enlarging brain metastases, and have not used steroids for brain metastases for at least 28 days prior to study initiation as per local site assessment. This exception does not include carcinomatous meningitis, as participants with carcinomatous meningitis are excluded regardless of clinical stability.

If brain imaging is performed to document the stability of existing metastases, MRI should be used if possible. If MRI is medically contraindicated, CT with contrast is an acceptable alternative.

### **8.2.1.2 Tumor Imaging During the Study**

The first on-study imaging assessment should be performed at 9 weeks (63 days  $\pm$  7 days) from the date of allocation. Subsequent tumor imaging should be performed every 9 weeks (63 days  $\pm$  7 days) for the first 12 months on treatment, or more frequently if clinically indicated. After 12 months on treatment, subsequent tumor imaging should be performed every 12 weeks (84 days  $\pm$  14 days), or more frequently if clinically indicated. Imaging timing should follow calendar days and should not be adjusted for delays in cycle starts. Imaging should continue to be performed until disease progression is identified by the

investigator, the start of new anticancer treatment, withdrawal of consent, or death, whichever occurs first.

Objective response should be confirmed by a repeat imaging assessment. Tumor imaging to confirm PR or CR should be performed at least 4 weeks after the first indication of a response is observed. Participants will then return to regular scheduled imaging every 9 weeks, starting with the next scheduled imaging time point. Participants who receive additional imaging confirmation do not need to undergo the next scheduled tumor imaging if it is less than 4 weeks later; tumor imaging may resume at the subsequent scheduled imaging time point. Note that the response does not typically need to be verified in real time by BICR.

### **8.2.1.3 End of Treatment and Follow-up Imaging**

For participants who discontinue study intervention, tumor imaging should be performed at the time of intervention discontinuation ( $\pm 4$  week window). If previous imaging was obtained within 4 weeks prior to the date of discontinuation, then imaging at intervention discontinuation is not mandatory. For participants who discontinue study treatment due to documented disease progression, this is the final required tumor imaging.

For participants who discontinue study treatment without documented disease progression, every effort should be made to continue monitoring disease status by radiologic tumor until the start of a new anticancer treatment, documented disease progression, pregnancy, death, withdrawal of consent, or the end of the study, whichever occurs first. The timing for these assessments should continue the same imaging schedule from the treatment phase (9 weeks  $\pm 7$  days in the first 12 months, or 12 weeks  $\pm 14$  days beyond 12 months – see Section 8.2.1.2); Imaging should occur at any time where there is clinical suspicion of PD.

### **8.2.2 RECIST 1.1 Assessment of Disease**

RECIST 1.1 will be used by the investigator as the primary measure for assessment of tumor response, date of disease progression, and as a basis for all protocol guidelines related to disease status (eg, discontinuation of study treatment). Although RECIST 1.1 references a maximum of 5 target lesions in total and 2 per organ, this protocol allows a maximum of 10 target lesions in total and 5 per organ, if clinically relevant to enable a broader sampling of tumor burden.

Participants who show evidence of radiological PD by RECIST 1.1, as determined by the investigator, will be discontinued from the study (see [Table 8](#)).

Clinical stability is defined as the following:

- Absence of symptoms and signs indicating clinically significant progression of disease
- No decline in ECOG performance status

- No requirements for intensified management, including increased analgesia, radiation, or other palliative care

Any participant deemed clinically unstable should be discontinued from trial treatment at site-assessed first radiologic evidence of PD.

Table 8 Imaging and Treatment After First Radiologic Evidence of Progressive Disease

	Clinically Stable		Clinically Unstable	
	Imaging	Treatment	Imaging	Treatment
First radiologic evidence of PD by RECIST 1.1	Repeat imaging at 4 to 8 weeks to confirm PD	May continue study treatment at the local site investigator's discretion while awaiting confirmatory tumor imaging by site.	NA	Discontinue treatment
NA = not applicable; PD = progressive disease; PFS = progression-free survival				

### 8.2.3 Eastern Cooperative Oncology Group (ECOG) Performance Scale

The investigator or qualified designee will assess ECOG status at the Screening Visit, prior to the administration of each dose of study intervention and during the Post-treatment Follow-up Phase as specified in the SoA (Section 1.3).

### 8.3 Safety Assessments

Details regarding specific safety procedures/assessments to be performed in this study are provided. The total amount of blood/tissue to be drawn/collected over the course of the study (from prestudy to poststudy visits), including approximate blood/tissue volumes drawn/collected by visit and by sample type per participant, can be found in the Study Procedures Manual.

Planned time points for all safety assessments are provided in the SoA.

#### 8.3.1 Physical Examinations

A complete physical examination will be conducted by an investigator or medically qualified designee (consistent with local requirements) as per institutional standard. Height and weight will also be measured and recorded.

A brief directed physical examination will be conducted by an investigator or medically qualified designee (consistent with local requirements) per institutional standard.

Investigators should pay special attention to clinical signs related to previous serious illnesses.

### **8.3.1.1 Full Physical Examination**

The investigator or qualified designee will perform a complete physical exam during the Screening phase. Clinically significant abnormal findings should be recorded as medical history. The time points for full physical exams are described in the SoA (Section 1.3). After the first dose of study intervention, new clinically significant abnormal findings should be recorded as AEs.

### **8.3.1.2 Directed Physical Examination**

The investigator or qualified designee will perform a directed physical exam as clinically indicated prior to trial treatment administration at the time points indicated in the SoA (Section 1.3). New clinically significant abnormal findings should be recorded as AEs.

### **8.3.2 Full Ophthalmic Examination**

Full ophthalmic examination, including best corrected visual acuity for distance testing, automated visual field testing, slit lamp examination, intraocular pressure and dilated funduscopy with attention to retinal abnormalities, especially retinal pigment epithelial detachment (RPED), serous detachment of the retina and RVO, will be performed by an ophthalmologist at the Screening Visit, C2D1 and then every 8 weeks from C2D1 and EoT. An ophthalmic examination at the Safety Follow-up Visit is only required if there was a clinically significant abnormality noted at EoT. For all participants, ophthalmic assessments may be performed more frequently per SOC or if clinically indicated for evaluation of any visual signs or symptoms.

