### 1.3.2 Dose Escalation: End of Treatment and Post-Treatment

Study Period: Treatment Cycle (C) / Visit:	End of Treatment (EoT) Discontinuation	Post-treatment			Notes
		Safety Follow-up	Follow-up Visits	Survival Follow-up	
Collection Timepoint: (Study Day [D])	At time of Treatment Discontinuation	30 days Post-last dose	Every 9 or 12 weeks Post-discontinuation	Every 12 weeks Post-last dose	
Scheduling Window (Days):	+7	+14	±7	±14	
Administrative Procedures					
Prior and Concomitant Medication Review	X	X			
Efficacy Assessments					
Tumor Imaging	X		X		In participants who discontinue study therapy without documented PD, tumor imaging should continue in Post-treatment Follow-up Visits, following the same imaging schedule from the treatment phase; and as clinically indicated.
Clinical Procedures/Assessments					
Review Adverse Events	X	X	X		Follow-up Visits: AEs will be collected when participant is in the clinic for tumor imaging assessment.
Full Physical Examination	X				
Full Ophthalmic Examination	X	X			Performed at the EoT. An ophthalmic examination at the Safety Follow-up Visit is only required if there was a clinically significant abnormality noted at EoT
Weight and Vital Signs	X				Vital signs: temperature, pulse, respiratory rate, and blood pressure
12-Lead Electrocardiogram	X	X			
Echocardiogram/ MUGA scan (Q12W)	X				
ECOG Performance Scale	X	X			
Post-study Anticancer Therapy Status			X	X	
Survival Status	X	X	X	X	All participants will be followed up for survival every 12 weeks (± 14 days) after discontinuation (unless consent is withdrawn). In addition, upon Sponsor request, participants may be contacted for survival status at any time during the study.

Study Period:	End of Treatment (EoT)	Post-treatment			Notes
Treatment Cycle (C) / Visit:	Discontinuation	Safety Follow-up	Follow-up Visits	Survival Follow-up	
Collection Timepoint: (Study Day [D])	At time of Treatment Discontinuation	30 days Post-last dose	Every 9 or 12 weeks Post-discontinuation	Every 12 weeks Post-last dose	
Scheduling Window (Days):	+7	+14	±7	±14	
LOCAL Laboratory Assessments					
CBC with Differential	X	X			
Chemistry Panel	X	X			Specific to creatinine: Cystatin C could be evaluated if creatinine is abnormal. Cystatin C may be conducted by central vendor only if analysis was not available from local study site laboratory.
Urinalysis	X	X			
Serum Tumor Marker	X	X			Collected as appropriate for tumor type.
CENTRAL Laboratory Assessments					

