### 3 HYPOTHESIS, OBJECTIVES, AND ENDPOINTS

There are no hypotheses for the study.

This study is to be conducted in male and female participants with advanced/metastatic solid tumors.

Objectives	Endpoints
Primary	

 
To determine the safety and tolerability and to establish preliminary RP2D(s) for the MK-8353 and selumetinib combination in participants with advanced/metastatic solid tumors
 
	
 
DLTs
 
AEs
 
Study drug discontinuations due to an AE
 

Secondary	

 
To evaluate the pharmacokinetics (PK) of MK-8353 and selumetinib
 
	
 
Pharmacokinetic parameters, including AUC, Cmin and Cmax
 

Tertiary/Exploratory	

 
To evaluate the overall response rate (ORR) and progression-free survival (PFS) based on RECIST 1.1 as assessed by the investigator for each dose level, and overall survival (OS).
 
	
 
OR (overall response): participants who have a confirmed complete response (CR) or partial response (PR)
 
PFS: time from the first dose of study medication to the first documented disease progression or death due to any cause, whichever occurs first.
 
OS: time from the first dose of study medication to death due to any cause.
 

 
To evaluate the serum levels of protein biomarkers (eg, carcinoembryonic antigen) before and after administration of MK-8353 in combination with selumetinib
 
	
 
Determination of molecular/proteomic markers indicative of clinical response, safety or mechanism of action of MK-8353 and selumetinib
 

 
To identify molecular (genomic, metabolic and/or proteomic) biomarkers that may be indicative of clinical response/resistance, safety, pharmacodynamic activity, and/or the mechanism of action of MK-8353 in combination with selumetinib
 
	
 
Germline genetic variation, genetic (DNA) mutations from tumor, tumor and blood RNA variation, proteomics and immunohistochemistry (IHC), and other biomarkers (F-fluoro-deoxy-glucose positron emission tomography [FDG-PET])
 

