### 4.3.3 Rationale for Dose Interval and Study Design

MK-8353 will have 50 mg incremental dose levels up to 250 mg (50, 100, 150, 200, 250 mg BID). Selumetinib will have 25 mg incremental dose levels up to 125 mg (25, 50, 75, 100, and 125 mg BID). These follow incremental increases of 100%, 50%, 33% and 25%. The smaller increases at higher doses take into consideration the risk for greater overlapping toxicity.

An alternate dose level, frequency drug administration and dosing schedule may be explored, and an optimal dose will be selected based on totality of data (PK, pharmacodynamic, and safety) emerging throughout the trial. The protocol will be amended as required.

The 4 days on/3 days off schedule was selected based on 1) a preclinical evidence that 4 days on/3 days off with vemurafenib (RAFi), trametinib (MEKi), SCH984 (ERKi) which was shown to ameliorate toxicity and sustain efficacy [Xue, Y., et al 2017]. In this study, continuous MEK/ERK/BRAFi administration was toxic and sequential ERK/MEK inhibition fosters resistance and was less effective, 2) the most common safety signal we see for MAPK pathway is skin rash, usually start seeing early time like from approximately 7 days after the treatment and within 3 month [Wang, D., et al 2007], 3) the short half-life of selumetinib and MK-8353 (approximately 8 hours) suggests that selumetinib and MK-8353 would be eliminated in as long as 2 days after stopping treatment, therefore, have the potential advantage to exploit intermittent schedules that have (preclinically) been shown to ameliorate toxicity but maintain anti-tumor activity [Xue, Y., et al 2017].

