## 6.6.2 Definition of Dose limiting Toxicity

All toxicities will be graded using NCI CTCAE v4.0 based on the investigator assessment.

The DLT window of observation will be during Cycle 1. The observation window can be modified to encompass Cycle 1 and 2 (and/or additional cycles).

The occurrence of any of the following toxicities during Cycle 1 will be considered a DLT, if assessed by the investigator to be possibly, probably, or definitely related to study treatment administration.

1. Grade 4 nonhematologic toxicity (not laboratory).
2. Grade 4 hematologic toxicity lasting  $\geq 7$  days, except thrombocytopenia:
  - Grade 4 thrombocytopenia of any duration
  - Grade 3 thrombocytopenia associated with clinically significant bleeding
3. Any nonhematologic AE  $\geq$  Grade 3 in severity should be considered a DLT, with the following exceptions: Grade 3 fatigue lasting  $\leq 3$  days; Grade 3 diarrhea, nausea, or vomiting without use of anti-emetics or anti-diarrheals per SOC lasting  $< 72$  hours; Grade 3 rash without use of corticosteroids or anti-inflammatory agents per SOC.
4. Any Grade 3 or Grade 4 non-hematologic laboratory value if:
  - Clinically significant medical intervention is required to treat the subject, or
  - The abnormality leads to hospitalization, or
  - The abnormality persists for  $\geq 72$  hours.
  - The abnormality is consistent with drug-induced liver injury and meeting the protocol Events of Clinical Interest criteria (see Section 8.4.7)

Exceptions: Clinically nonsignificant, treatable, or reversible laboratory abnormalities including liver function tests, uric acid, etc.

5. Febrile neutropenia Grade 3 or Grade 4:
  - Grade 3 is defined as absolute neutrophil count (ANC) <1000/mm^3 with a single temperature of >38.3 degrees C (101 degrees F) or a sustained temperature of ≥38 degrees C (100.4 degrees F) for more than 1 hour
  - Grade 4 is defined as ANC <1000/mm^3 with a single temperature of >38.3 degrees C (101 degrees F) or a sustained temperature of ≥38 degrees C (100.4 degrees F) for more than 1 hour, with life-threatening consequences and urgent intervention indicated.
6. An elevated AST or ALT laboratory value that is ≥3X the ULN and an elevated total bilirubin laboratory value that is ≥2X the ULN and, at the same time, an alkaline phosphate laboratory value that is <2X the ULN, as determined by the way of protocol-specified laboratory testing or unscheduled laboratory testing.

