7. Prolonged delay (>2 weeks) in initiating Cycle 2 due to treatment-related toxicity.
8. Any treatment-related toxicity that causes the participant to discontinue treatment during Cycle 1.
9. Missing >25% of MK-8353 and/or selumetinib doses as a result of drug-related AE(s) during the first cycle.
10. Grade 5 toxicity.
11. Cardiac disorders
  - Absolute decrease in LVEF >10% compared with baseline and the LVEF is below the institution's lower limit of normal
  - Left ventricular systolic dysfunction Grade ≥3
  - Other cardiac disorders Grade ≥3
12. Vascular disorders
  - Hypertension CTCAE Grade ≥3 requiring more than 1 drug or more intensive therapy
  - Grade 4 hypertension

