### 13. Eye disorders

#### Retinal:

- Retinopathy or retinal detachment Grade  $\geq 2$ , confirmed by ophthalmic examination
- Retinal vein disorder including retinal vein occlusion, confirmed by ophthalmic examination

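### No eye examination is scheduled inside the 21-day DLT window, and the plan does not say whether C2D1 retinal findings count as Cycle 1 DLTs or must be known before the next level opens

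*Combined protocol and SAP*

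**What the plan says.** - **Eye examinations (Section 8.3.2).** They "will be performed by an ophthalmologist at the Screening Visit, C2D1 and then every 8 weeks from C2D1 and EoT". Beyond that, "ophthalmic assessments may be performed more frequently per SOC or if clinically indicated for evaluation of any visual signs or symptoms". Section 8.3.3 adds imaging when a retinal abnormality is suspected clinically.
- **DLT window (Section 6.6.2).** "The occurrence of any of the following toxicities during Cycle 1 will be considered a DLT", given a possible, probable or definite relation to treatment. The window may be widened to later cycles, but no trigger is stated.
- **Retinal DLTs (Section 6.6.2, criterion 13).** Retinopathy or retinal detachment counts from Grade 2 upward when an eye examination confirms it. The second item has no grade threshold: "Retinal vein disorder including retinal vein occlusion, confirmed by ophthalmic examination".
- **Opening the next level (Section 6.3.1).** Each sequence moves on as soon as the 21-day observation period of the previous level is complete.
- **Who is counted (Sections 4.3.4 and 9.5.1).** The DLT-evaluable set is participants who finished Cycle 1 without a DLT or had one in Cycle 1. Having had an eye examination is not a condition.
- **LVEF (Section 6.6.2, criterion 11).** "Absolute decrease in LVEF >10% compared with baseline and the LVEF is below the institution's lower limit of normal" is a DLT, with no symptom required. Section 8.3.6 refers scan timing to the Schedule of Activities.

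**The concern.** The plan makes certain retinal findings dose-limiting and requires an examination to establish them. It then places the first scheduled on-treatment examination nominally one day after the window closes, and lets the next level open when the window closes. A participant with a retinal change but no visual complaint can therefore be entered in Table 2 as having no DLT before anyone has looked.

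If the change is then found at C2D1, the text does not say whether the tally is revised. Table 7 ends treatment for retinal vein occlusion of any grade, so the plan regards the event as serious, yet it does not settle whether the event reaches the count that sets the dose. That same count feeds the isotonic DLT estimates and the choice of MTD in Sections 4.3.4 and 9.6.2.

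**Working it through.** **1. Calendar.** Section 4.3.2 states 6000 mg of MK-8353 per 3-week cycle at 250 mg BID, 4 days on and 3 days off. Dosing days in Days 1–21 are 1–4, 8–11 and 15–18, which is 12 days, and 250 × 2 × 12 = 6000 mg. The stated figure reproduces, so Cycle 1 is Days 1–21 and nominal C2D1 is Day 22. With the ±3-day window (SoA header and Section 6.6.3.1), C2D1 may fall on Days 22 − 3 = 19 to 22 + 3 = 25.

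**2. Scheduled examinations against the window.**
- Screening: before Day 1.
- C2D1: Day 22, permitted range Days 19–25.
- Next: 22 + 56 = Day 78.
- Scheduled nominally within Days 1–21: none. An examination on Days 19–21 is allowed but not required.

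**3. Table 2.** The table was rebuilt from its footnote (target 0.30, ε₁ = ε₂ = 0.03, Beta(1,1) prior), taking the decision with the largest unit probability mass and DU when P(rate > 0.30) exceeds 0.95. The 0.95 cutoff is an assumption, because the documents do not state it. All 93 cells checked (0 to 8 DLTs, n = 3 to 14) match, so the printed entries can be used as they stand.

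**4. Effect of one uncounted DLT.**

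| Full count | Decision | One not counted | Decision |
|---|---|---|---|
| 1/3 | S | 0/3 | E |
| 2/3 | D | 1/3 | S |
| 2/6 | S | 1/6 | E |
| 4/6 | DU | 3/6 | S |
| 1/6 | E | 0/6 | E |
| 3/6 | S | 2/6 | S |

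Four of these six cells change, each toward a less cautious decision.

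**5. Illustration over a range.** The documents give no rate for silent events. Suppose m percentage points of the true DLT rate come from participants whose only DLT goes uncounted, so the observed rate is q = true rate − m. Table 2 gives E at n = 3 only for 0 DLTs, and at n = 6 for 0 or 1:
- P(E, n = 3) = (1 − q)³
- P(E, n = 6) = (1 − q)⁶ + 6q(1 − q)⁵

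| True rate | n | m = 0 | m = 5 | m = 10 | m = 15 |
|---|---|---|---|---|---|
| 40% | 3 | 0.216 | 0.275 | 0.343 | 0.422 |
| 40% | 6 | 0.233 | 0.319 | 0.420 | 0.534 |
| 30% | 3 | 0.343 | 0.422 | 0.512 | 0.614 |
| 30% | 6 | 0.420 | 0.534 | 0.655 | 0.776 |

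These are chances of an E cell in a single cohort of that size, not operating characteristics of the whole design. With m = 0 there is no effect.

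**The case against.** The best defence is that Section 6.6.2 turns on when a toxicity occurs, not when it is detected. Between Screening and an examination done before the C2D1 dose, the only study-drug exposure is that of Cycle 1, and Section 6.6.3.1 puts predose procedures ahead of Day 1 dosing. An investigator could properly assign such a finding to Cycle 1. This stands. A reader might infer that a C2D1 finding is a Cycle 2 event and excluded as written, or that the schedule cannot pick up a retinal DLT at all; the text supports neither. It is silent, and Section 6.3.1 does not wait for the result.

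Other safeguards narrow the gap:
- Examinations per standard of care or for visual symptoms are allowed at any time.
- The general grade definitions in Appendix 3 put asymptomatic findings mainly in Grade 1, so retinopathy of Grade 2 or more would often cause symptoms and prompt an examination. The silent gap is chiefly retinal vein disorder.
- A delay of more than 2 weeks in starting Cycle 2 for related toxicity is itself a DLT, but shorter holds are not caught.
- The window can be extended, but nothing says when.
- Sections 4.1 and 4.3.4 call for ongoing safety review and for the totality of the data before an RP2D is chosen. That can correct a later choice of dose; it does not define the count used for escalation.

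A reader might also infer from the statement that "selumetinib and MK-8353 would be eliminated in as long as 2 days after stopping treatment" that a retinal change would have cleared by C2D1, after three drug-free days. Elimination of drug is not resolution of an event. Table 7 checks retinal events for resolution at 7 to 10 days, longer than three, and gives retinal vein occlusion no resolution branch.

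**Conclusion.** The concern holds as a gap between three sections. Section 8.3.2 schedules no eye examination within nominal Days 1–21, Section 6.6.2 needs one to confirm a retinal DLT in Cycle 1, and Section 6.3.1 clears the level when the 21 days end. The plan settles neither whether a pre-dose C2D1 finding counts nor whether escalation waits for it.

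The size per event is definite: one uncounted DLT changes the decision at 1/3, 2/3, 2/6 and 4/6. How often that would happen is unknown, and any stated chance that a cohort contains a silent event would rest on an assumed rate. The treatment-phase SoA row for eye examinations is not in the text supplied for review; the conclusion rests on Section 8.3.2, which lists the timings and names none in Cycle 1.

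For LVEF the point is conditional. A reader might infer from the Q12W label in the end-of-treatment table that the first on-treatment scan is at about Day 85 (1 + 84). An interval does not fix the first date, and the treatment-phase ECHO/MUGA row is also not in the supplied text. The documents as read do not establish an LVEF gap.

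**What to change.** Reconcile Sections 6.6.2, 6.3.1 and 8.3.2 using the examination already planned:

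- In 6.6.2, state that a qualifying retinal finding at the C2D1 examination, done before the C2D1 dose, enters the Cycle 1 DLT tally.
- In 6.3.1, state that a level is not cleared until the C2D1 examination results of its evaluable participants are in.
- In 8.3.2, state that the C2D1 examination precedes dosing, so that the attribution to Cycle 1 is clear.

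For criterion 11, check the treatment-phase ECHO/MUGA row. If no scan falls in or at the end of Cycle 1, reconcile criterion 11 with 6.3.1 and 8.3.6 in the same way.

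The change adds no examination and moves none; new examination days would be a monitoring schedule, which this point does not propose. The cost is a few sentences and a possible delay per level: nominally 22 − 21 = 1 day, up to 25 − 21 = 4 days if the full visit window is used, plus reporting time, and longer only where Cycle 2 itself is held.
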